Phase II study to evaluate the Efficacy and Safety of Sirolimus in subjects with metastatic, mismatch repair deficient solid tumors after immunotherapy.

Principal Investigator: [name]

Department of Medical Oncology

Albert Einstein College of Medicine/Montefiore Medical Center

[name]

Email: [contact]

Co- Investigators: [name]

Professor, Department of Cell Biology and Genetics

Albert Einstein College of Medicine

Michael F. Price Center

[name] E mail: [contact]

Study Statistician: [name]

Professor, Department of Epidemiology and Population Health

Albert Einstein College of Medicine Jack and Pearl Resnick Campus

[name]

[name]

Email: [contact]

Document version (date) Version 5.0 (01/2023)

Commercially available agent Sirolimus

TRIAL SCHEMA

[figure not shown]
"Open-label, Single arm Phase II study of Sirolimus in metastatic, mismatch-repair deficient solid tumors after immunotherapy"

Hypothesis: - Sirolimus improves ORR by 20% in patients with dMMR solid tumors

Primary Objective: -To evaluate the efficacy of sirolimus by estimating the ORR as assessed by RECIST 1.1 in dMMR solid tumors

Secondary Objectives: -To determine other efficacy mesures (PFS, OS) of sirolimus in dMMR solid tumors

-To assess safety of sirolimus trough evaluation of incidence and severity of adverse events by CTCAE.

Statistical Plan:

Effect size: 20% improvement in ORR (i.e., from 5% to 25%)

Power: 80% **Type 1 error:** 0.05

Expected drop-out rate: 15% Calculated N: 19 patients

Contents

1.	ABSTRACT	5
2.	INTRODUCTION	6
	2.1 Background	6
	2.2 mTOR signaling pathway in cancer	7
	2.3 Pre-clinical Data	7
	2.3.1 In-vitro data	7
	2.3.2 Animal model data	8
	2.4 Clinical experience with mTOR inhibitors	.11
	2.5. Relevance and Significance	.12
3.	OBJECTIVES	.12
	3.1 Primary objective:	.12
	3.2 Secondary objectives:	.13
4.	MATERIAL AND METHODS	.13
	4.1 Study design	.13
	4.2 Patient selection	.13
	4.2.1. Inclusion criteria	.13
	4.3 Treatment plan	.14
	4.4 Dosing delays/modifications	.15
	4.5 Response Evaluation Plan	.15
	4.6 Biomarker studies	.15
	4.6.1 Prior to treatment initiation:	.15
	4.6.2 During treatment:	.16
5.	STATISTICAL CONSIDERATIONS	.16
	5.1 Endpoints	.16
	5.1.1 Primary Endpoint	.16
	5.1.2 Secondary Endpoints	.16

	5.2.Sample size	17
	5.3.Analysis Plan	17
6.	ETHICAL CONSIDERATIONS	18
	6.1 Patient Recruitment	18
	6.2 Patient confidentiality	18

1. ABSTRACT

Despite recent therapeutic strategies, including immunotherapy, treatment alternatives for patients with metastatic mismatch-repair deficient (dMMR) solid tumors remain scarce. Pre-clinical data suggests that dMMR tumors are susceptible to rapamycin (sirolimus), a mTOR inhibitor. In these tumors, characterized by higher levels of oxidative stress, sirolimus can exert a cytotoxic effect, led by the failure to repair DNA damage by inhibition of antioxidant enzymes such as FOXO3a triggered by Akt hyperactivation.

This proposal presents a phase 2 clinical trial designed to evaluate the efficacy of sirolimus in patients with dMMR solid tumors after immunotherapy. We hypothesize that sirolimus will increase the overall response rate (ORR) by 20%. To detect such a difference with 80% power and a type-1 error rate of 0.05, 16 participants are required. Accounting for a 15% drop-out rate, we aim to enroll 19 subjects.

After informed consent, adult patients with histologically-proven metastatic solid cancer, dMMR by immunohistochemistry (IHC) or next-generation sequencing, a performance status of \leq 2 by ECOG, at least one measurable lesion based on Response Evaluation Criteria in Solid Tumors (RECIST v1.1), hemoglobin \geq 9 g/dL, absolute neutrophil count \geq 1,500 mm³, platelet count \geq 75,000 mm³, adequate liver and renal function (\leq G1 by CTCAE) will be eligible.

Sirolimus to reach a serum trough level target ≥ 8 ng/ml will be administered orally in 28-day cycles and will be continued until progression of disease evidenced by imaging, unacceptable toxicity or patient withdrawal. Imaging within 21 days of treatment initiation will be considered as baseline. Response to treatment will be assessed by imaging after 8 weeks of achieving therapeutic sirolimus levels, and every 8 weeks thereafter. ORR will be defined as the proportion of patients who achieve complete response or partial response, as assessed by our independent radiology team based on RECIST v1.1. Corresponding exact 95% confidence intervals will also be computed for the true ORR. Side effects will be evaluated and graded using CTCAE at every clinic visit and will be reported as frequencies.

Historical tumor samples will be requested for evaluation of potential biomarkers. In cases where archival samples are not available, an optional biopsy prior to treatment will be offered. All cases with available baseline biopsy, will be offered a repeated biopsy 8 weeks after achieving rapamycin serum target level. Expression levels of Akt, pAkt, Foxo3a, pFoxo3a and 8OxoG will be determined by IHC and reported as 1+ (low), 2+ (intermediate) or 3+ (high). An increase in biomarker expression will be

defined as a change from 1+ at baseline to 3+ after treatment for each specific biomarker. Tumor mutational burden and gene mutations will be evaluated by next-generation sequencing in baseline biopsies. Exploratory analysis will be performed to compare biomarkers between patients with and without objective response.

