3. OBJECTIVES

3.1 Primary objective:

 To evaluate the efficacy of sirolimus by estimating the overall response rate (ORR) as assessed by Response Evaluation Criteria In Solid Tumors versión 1.1 (RECIST v1.1) in patients with metastatic dMMR solid cancer after immunotherapy (either due to disease progression or to inability to tolerate treatment).

3.2 Secondary objectives:

- To assess potential tissue biomarkers (Akt, pAkt, FOXO3a, pFOXO3a, 80xoG expression by immunohistochemistry, tumor mutational burden/gene mutations by next-generation sequencing), the effect of sirolimus treatment on these biomarkers, and possible correlation between these biomarkers and clinical response.
- To evaluate other clinical end-points such as progression-free survival, response duration and overall survival of sirolimus in patients with metastatic dMMR solid cancer after immunotherapy (either due to disease progression or to inability to tolerate treatment).
- To evaluate tolerability and safety of sirolimus using Common Terminology
 Criteria for Adverse Events (CTCAE) grading scale.

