4.6 Biomarker studies

4.6.1 Prior to treatment initiation:

- Historical tumor samples will be requested for all participants for evaluation of potential biomarkers. In cases where archival biopsies are not available, the patient will be offered a biopsy prior to treatment initiation. This will be optional and will not affect enrollment into the clinical trial. These samples will be used to evaluate the baseline expression of Akt, pAkt, FOXO3a, pFOXO3a, 80xoG expression will be evaluated by immunohistochemistry in the laboratory of [name].
- We anticipate that most of the patients would have had next-generation sequencing requested before our evaluation, so, the results will be directly requested. In cases where it was not done; it will be ordered. This will be used to

explore potential mutations that could correlate with treatment response.

4.6.2 During treatment:

• Repeated biopsies after 8 weeks of treatment will be offered to all participants that had an evaluable biopsy prior to treatment initiation. This will be optional and will not affect continuation into the clinical trial. Changes in the expression of Akt, pAkt, FOXO3a, pFOXO3a, 80xoG expression will be evaluated by immunohistochemistry in the laboratory of [name].

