5.3 Analysis Plan

The ORR will be estimated as the proportion of patients with metastatic dMMR solid cancer refractory to immunotherapy who achieved the endpoint of objective response after treatment with sirolimus. Corresponding exact 95% confidence intervals will also be computed for the true ORR. The distribution of progression-free survival and overall survival will be estimated using the Kaplan-Meier method. Greenwood's method will be applied to estimate confidence intervals.

As a secondary aim, we will evaluate other clinical efficacy end-points such as PFS (time from target serum sirolimus levels to progression of known metastases or new metastatic site, or death from any cause), response duration (time from documentation of tumor response to disease progression.) and overall survival (OS, time from target serum sirolimus levels to death from any cause). The distribution of PFS, DR and OS will be estimated using the Kaplan-Meier method. Greenwood's method will be applied to estimate confidence intervals.

Provided the number of patients who achieve objective response is sufficient, exploratory analyses to assess the association between ORR and the expression of tissue biomarkers will be performed. An exact test for trend for ordered contingency tables will be used to compare the frequency of subjects with low, moderate and high biomarker expression between patients with and without objective response; Fisher's exact test will be used to compare the frequency of subjects that had an increase in biomarker expression after treatment between patients with and without objective response. Gene mutations will be reported as frequencies and compared between patients with and without objective response by Fisher's exact test. The two sample Wilcoxon rank sum or T-test will be conducted to compare the tumor mutational burden between patients with and without objective response.

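### Section 5.3 analyses biomarker change only by response status, only if responders are numerous enough, and on a definition that counts 1+ to 3+ alone; the secondary objective on the effect of sirolimus needs an unconditional grade-shift table

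*Combined protocol and SAP*

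**What the plan says.** All references are to the combined protocol and SAP.

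- **Objective (section 3.2).** One secondary objective covers the markers themselves, "the effect of sirolimus treatment on these biomarkers, and possible correlation between these biomarkers and clinical response". The effect of treatment and the correlation with response are listed as separate aims.
- **Scale and definition (section 1, Abstract).** Each marker is graded 1+, 2+ or 3+. An increase is "defined as a change from 1+ at baseline to 3+ after treatment for each specific biomarker". Section 5.3 uses the word increase without defining it again.
- **Sampling (sections 4.6.1 and 4.6.2).** For baseline, "Historical tumor samples will be requested for all participants for evaluation of potential biomarkers"; a fresh biopsy is offered only where no archival tissue exists. On treatment, "Changes in the expression of Akt, pAkt, FOXO3a, pFOXO3a, 80xoG expression will be evaluated by immunohistochemistry". Of the repeat biopsy the plan says: "This will be optional and will not affect continuation into the clinical trial".
- **Analysis (section 5.3).** The biomarker paragraph begins "Provided the number of patients who achieve objective response is sufficient, exploratory analyses to assess the association between ORR" and marker expression. It sets no threshold. An exact trend test is to "compare the frequency of subjects with low, moderate and high biomarker expression between patients with and without objective response". Fisher's exact test is to "compare the frequency of subjects that had an increase in biomarker expression after treatment between patients with and without objective response". The remaining comparisons, on gene mutations and tumor mutational burden, are also by response.

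**The concern.** Whether sirolimus shifts a marker is a within-patient question and needs no responders. Section 2.3.2 predicts rises in pAkt, pFOXO3a and 8-oxoG under rapamycin, and section 2.5 relies on the tissue markers to confirm a cytotoxic effect. Yet the one specified analysis of change depends on having responders, and it reduces nine possible grade pairs to a yes/no in which a single cell is yes.

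Two things are at stake. If sirolimus produces few responses, the paired grades would help to show whether the pathway was engaged, but that is when the only planned analysis of change is likely to be dropped. If there are enough responders, patients whose marker rose by one grade are grouped with those whose marker was flat or fell. In either case the summary of change would be chosen after the data are seen.

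**Working it through.** **1. The plan's own figures (section 5.2).** Exact binomial, success if at least 3 of 16 respond:
- P(X ≥ 3 | 16, 0.05) = 0.043, within the stated 5%.
- P(X ≥ 3 | 16, 0.25) = 0.803, meeting the stated 80%.
- 16 / 0.85 = 18.8, rounded up to 19 enrolled.

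These reproduce. The documents give no sample size or power for the biomarker objective.

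**2. What the definition counts.** A three-grade scale gives 3 × 3 = 9 baseline-to-follow-up pairs. Three are rises: 1+ to 2+, 2+ to 3+ and 1+ to 3+. Only the last is an increase under the Abstract. The share of tumors that can rise is the share at 1+ or 2+; the share that can be counted is the share at 1+. Baseline grades are not given, so the splits below are illustrative:

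| Baseline 1+/2+/3+ | Can rise | Can be counted |
|---|---|---|
| even thirds | 67% | 33% |
| 20/40/40 | 60% | 20% |
| 60/30/10 | 90% | 60% |

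**3. How often the comparison by response has no responders.** P(0 responders) = (1 − ORR)^n:

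| n | ORR 5% | ORR 25% |
|---|---|---|
| 16 (all evaluable) | 0.95^16 = 44% | 0.75^16 = 1% |
| 8 pairs (assumed) | 66% | 10% |
| 5 pairs (assumed) | 77% | 24% |

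The rows for 8 and 5 pairs also assume that having a paired biopsy is unrelated to response. Zero is the extreme case. If the threshold were 3 responders among 16 (illustrative, as the plan gives none), the comparison would be skipped with probability 1 − 0.043 = 95.7% at an ORR of 5% and 1 − 0.803 = 19.7% at 25%. With a single responder, perfect separation gives a smallest Fisher p of 1/16 = 0.0625 with 16 pairs and 1/8 = 0.125 with 8.

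**4. What a within-patient analysis could deliver.** Exact 95% intervals for the proportion rising: 4 of 8 gives 16% to 84%; 8 of 16 gives 25% to 75%. For a two-sided exact sign test on m changed pairs, the smallest p is 2 × 0.5^m: 0.0625 at m = 5 and 0.031 at m = 6. If 40% of pairs rise and none fall (assumed), power is 5% with 8 pairs and 67% with 16. A table with intervals is therefore the useful output, and a test adds little.

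**5. The time point.** The Abstract places the repeat biopsy 8 weeks after the target serum level is reached. Section 4.6.2 places it after 8 weeks of treatment. Dosing is titrated to the target level, so these can be different dates, and a paired comparison needs one.

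**The case against.** The strongest reply is that nothing essential is missing. The Abstract and section 4.6.2 say, with no condition on responders, that grades will be reported and changes evaluated. The condition in section 5.3 attaches to the association with response, where it is reasonable, and that paragraph is labelled exploratory. A strict 1+ to 3+ cut-off is defensible when the default baseline is archival tissue, because one-grade differences may reflect the reader or the sample. A paired test would be nearly uninformative at plausible pair counts.

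Much of this stands. A reader might infer that the plan ignores change altogether, or that the cut-off is an error. The documents support neither reading: the intention to report and evaluate is stated, and a strict cut-off has a purpose even though none is given. The low power of a paired test is also conceded.

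What does not fall away is narrower. Stating that changes will be evaluated by immunohistochemistry names the assay, not how paired grades will be summarised. The exploratory label is applied to the association with response, while section 3.2 places the treatment effect under secondary objectives. The trend test uses all three grades, but on expression level rather than change. And a stated rule, not a missing detail, scores two of the three possible rises as no increase.

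**Conclusion.** The point holds as a minor one and a cheap improvement. The effect of sirolimus on the markers is part of a secondary objective, but its only specified analysis is by response, conditional on an undefined number of responders, and blind to one-grade rises.

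It rests on reading the Abstract's definition into section 5.3, which is the only definition available. The 44% and 1% follow from the plan's own ORR values and 16 evaluable patients. Pair counts, baseline splits and rise rates are assumptions. Independence of pairing and response is doubtful, because the repeat biopsy falls near the first response scan and treatment stops at progression.

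Two further inferences are not supported. The primary result is not at risk: no decision rule uses the biomarkers, and the ORR test and 3-of-16 rule are untouched. Nor would a better paired analysis show an effect limited to dMMR tumors, as section 2.5 hopes. No pMMR tumors are enrolled, and section 2.3.2 reports pAkt and pFOXO3a rising in both types of cell line, with only 8-oxoG confined to dMMR.

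**What to change.** In section 5.3:

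- For each marker, and regardless of the number of responders, report the full 3x3 baseline-by-post-treatment grade table for all paired samples, with the proportions rising and falling by any grade and exact 95% confidence intervals. Make this the main output for the treatment-effect part of the objective.
- Treat any paired test, for example an exact sign test, as optional, exploratory and unadjusted, and note that it cannot reach 0.05 with 5 or fewer changed pairs. Five independent tests at 0.05 would carry a 1 − 0.95^5 = 23% chance of at least one false positive.
- In the comparison by response, replace the yes/no increase with the ordinal grade change, using the exact trend test already named. State in advance how many responders it requires.
- Keep 1+ to 3+ as a descriptive large increase, with the reason for the cut-off.
- Show archival and fresh baselines separately, and do not attribute shifts to sirolimus alone.
- Reconcile the repeat-biopsy time point between the Abstract and section 4.6.2.

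The cost is a few sentences and a few lines of analysis on samples already planned, with no extra patients or biopsies. The downside is that one-grade changes are more exposed to reader and sample-source noise, which is why the 1+ to 3+ category and the split by baseline source should be shown alongside.

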2. INTRODUCTION

2.1 Background

Deficient mismatch repair (dMMR) is a molecular fingerprint that results from the accumulation of mutations at DNA elements named microsatellites which are characterized by short nucleotide-repetitive sequences in the coding or non-coding regions (1). dMMR has been reported in different solid cancer types with an estimated frequency of 2.2% among more than 50 different cancer types; most commonly represented by colorectal and endometrial cancer (2). It can present as hereditary or sporadic (2). In the former, it is driven by a germline mutation in the mismatch repair (MMR) genes which predispose to colorectal cancer (CRC), endometrial cancer and others such as pancreatic, gastric, urinary tract, brain and skin cancer in Lynch syndrome (3). In the latter, dMMR is generated by a biallelic somatic mutation in the MMR genes or by epigenetic changes, which most commonly cause MLH1 promoter hypermethylation. (4) (5).

Independent of cancer type, dMMR tumors showed an important overall response rate (ORR) with an extended duration of response to programmed-death ligand 1 (PDL1) inhibitors such as pembrolizumab (6). Prior studies have reported ORRs ranging between 31-47.9% and durable responses of more than 6 months in two-thirds of responders. Consequently, pembrolizumab was approved in 2017 by the United States Food and Drug Administration (USFDA) for adult and pediatric patients with unresectable or metastatic dMMR solid tumors that had exhausted other therapeutic options (7). However, treatment options for patients with dMMR solid cancer after immunotherapy, due to progression of disease or inability to tolerate treatment for immune-related adverse events, are limited and represent the focus of current pre-clinical and clinical studies.

2.2 mTOR signaling pathway in cancer

mTOR is a serine/threonine kinase that belongs to the phosphoinositide 3-kinase related protein kinase (PIKK) family and has two different complexes named mTOR complex-1 (mTORC1) and mTOR complex-2 (mTORC2). mTOR signaling regulates cell growth, metabolism, proliferation and survival through activation of transcriptional factors and inhibition of autophagy. It has been reported that this pathway is overactivated in more than 70% of cancers (8). Consequently, mTOR inhibitors have been developed with currently 3 different FDA-approved drugs in the market: sirolimus, temsirolimus and everolimus. This phase 2 trial will study the prototype mTOR inhibitor, sirolimus, which is a direct mTORC1 inhibitor.

mTORC1 has important components such as the associated protein regulator named RAPTOR and the negative regulator called PRAS40. mTORC1 pathway can be activated via the PI3K/AKt pathway or the ras-MAPK pathway as a response to different stimuli including oncogenic growth factors, insulin, nutrients and hypoxia. In the former, Akt induces phosphorylation that leads to dissociation and inactivation of the TSC2/TSC1 complex that negatively regulates RHEB, an mTORC1 activator. Additionally, Akt can directly phosphorylate and inactivate PRAS40, which releases RAPTOR that activates mTORC1. In the latter, the ras-MAPK pathway causes activation of MEK 1/2, ERK 1/2 and RSK which can phosphorylate TSC2 causing its dissociation from TSC1 leading to mTORC1 activation (8).

The overactivation of mTOR signaling in cancer follows three different mechanisms:

1) mutations in the mTOR gene; 2) mutations in the components of mTORC1 and mTORC2 or 3) Mutations in suppressor genes or oncogenes. In this regard, PTEN is a tumor suppressor gene that blocks the PI3K pathway. Mutations of PTEN are commonly reported in different solid tumors and are frequently mutated in dMMR tumors (8).

[figure not shown]
2.3 Pre-clinical Data

2.3.1 In-vitro data

Vilar et al. analyzed 5 different gene expression signatures in CRC aiming to compare the gene expression profile between dMMR and pMMR CRC tumors. This information was used to create an intersection signature, which included genes that were differentially expressed in all the signatures, and a union signature, which included genes that were differentially expressed in any signature. A connectivity map was used to select candidate compounds from 164 tested compounds which allowed the

recognition of 2 drugs (rapamycin and a phosphoinositide 3-kinase named LY-294002) that were selected for testing in-vitro using 8 CRC cell lines. Of these, 2 were pMMR (HT-29 and SW-480) and 6 were dMMR (HCT-116 and Lovo that had MLH1 and MSH2 mutations; HCT-15 and HCT-8 that had MSH6 mutation; SW-48 and RKO that displayed hypermethylation in the promoter of MLH1 gene).

At rapamycin concentrations ranging from 0.6 to 17 uM, **5 of 6 dMMR CRC cell lines** were sensitive to mTOR inhibition compared to MSS cell lines with a **6x difference in IC50** (p=0.002). Of note, cell lines with mutation in the MMR proteins MSH2 and MSH6 were the most sensitive to mTOR inhibition. These results were confirmed in proliferation data and highlighted the potential relevance of mTOR inhibition as a targeted therapy among dMMR CRC tumors (Figure 1).

[figure not shown]

